#### 7.5 SECONDARY ASSESSMENTS

The secondary assessments will be conducted on the ES.

For each participant, the C-PPAC difficulty domain score is first calculated as a raw score by summing up the numerical answers to questions 3-12 (ignoring missing values); the range of raw score is 0-40. The raw score will then be scaled to a 0-100 Rasch scaled score (with 0 being the worst and 100 the best). The change from baseline in the scaled score of the C-PPAC difficulty domain at Week 12 will be reported. More details about the C-PPAC difficulty domain score calculation appear in Section 10.2.

The activity tracker ( watch) will record steps taken by the participants and time.

- A "valid day" is defined as a day where the activity tracker records at least 8 active hours during waking hours (7am to 10pm local time for the participant).
- Only activities between 7am to 10 pm local time will be analyzed. All times are collected in UTC and will have to be converted into local times.
- To calculate the average number of steps at baseline, the data from the prior 14 days is examined. At least 4 valid days out of the 14 days are needed for analysis, but they do not have to be consecutive days.
- If there are fewer than 4 valid days, the average number of steps at baseline will not be calculated.
- The number of steps taken is summed up for all the valid days, then averaged over the number of valid days, and that represents the average number of steps measured by the activity tracker at baseline.
- The same process is repeated for Week 12, to calculate the average number of steps at Week 12 (if there exist at least 4 valid days in the 14 days prior to Week 12).
- The change from baseline in the average number of steps measured by the activity tracker at Week 12 will be reported for each participant.
- The "walking duration" (in minutes per day) will be calculated from the start and stop times of the activity tracker's recorded activity for each valid day.
- The cadence (in steps/min) for a valid day will be calculated as the number of steps per day divided by the walking duration.
- The average cadence (in steps/min) measured by the activity tracker at baseline will be calculated as the average of cadence for all valid days 14 days prior to baseline.
- The average cadence (in steps/min) measured by the activity tracker at Week 12 will be calculated as the average of cadence for all valid days 14 days prior to Week 12.
- The change from baseline in the average cadence (steps/min) measured by the activity tracker at Week 12 will be reported.

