5.1.2 Secondary Assessments

Activity Tracker (device)

A physical activity tracker is an accelerometer that is used to measure the overall movement of a patient. Activity trackers provide valuable information on physical activity directly from the patient's body.

The device will be the activity tracker used in the study to measure the amount (steps) and intensity (cadence) of daily ambulatory activities in support of the main research objective. Participants will wear the activity tracker throughout the study and the data obtained from the activity tracker will be transferred to the study database.

Instructions will be given to the participants on how to use the activity tracker.

Clinical Visit PROactive Physical Activity in COPD instrument (C-PPAC)

A secondary measure of efficacy is the C-PPAC, a hybrid measurement tool incorporating a patient-reported outcome (PRO) and an activity tracker. The tool couples the difficulties associated with performing physical activity and the amount and intensity of the activities and the final instrument incorporates both a difficulty domain consisting of 10 questions and an amount domain consisting of 4 questions and 2 of these questions are based on data from the activity tracker.

The difficulty domain includes questions related to breathlessness, but also includes questions related to other aspects of the difficulty associated with performing daily activities in IwCOPD.

The C-PPAC should be completed by the participants at the time points outlined in the flow chart. Details of the C-PPAC are provided in Appendix 10.2.2.

16 Sep 2021

Clinical Study Protocol Outline Page 33 of 93

Proprietary confidential information © 2021 Boehringer Ingelheim International GmbH or one or more of its affiliated companies

16 Sep 2021

Clinical Study Protocol Outline Page 34 of 93

Proprietary confidential information © 2021 Boehringer Ingelheim International GmbH or one or more of its affiliated companies

16 Sep 2021

Clinical Study Protocol Outline Page 35 of 93

Proprietary confidential information © 2021 Boehringer Ingelheim International GmbH or one or more of its affiliated companies

16 Sep 2021

Clinical Study Protocol Outline Page 36 of 93

Proprietary confidential information © 2021 Boehringer Ingelheim International GmbH or one or more of its affiliated companies

Page 37 of 93

16 Sep 2021

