#### 4. CHANGES IN THE PLANNED ANALYSIS OF THE STUDY

As a result of the limited sample size (5 instead of the planned 50 individuals with chronic obstructive pulmonary disease (IwCOPD), the pre-planned analyses for this study will not be conducted. Instead, listings of participants' data will be generated for inclusion in an abbreviated study report. The primary and secondary assessments will be listed for each participant, and from the further assessments, only the engagement with TARA will be listed. No subgroup analyses will be performed.

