#### 7. PLANNED ANALYSIS

All the assessments (primary, secondary and further), as well as the demographics and baseline characteristics, will be presented as listings for participants, on the ES.

Customized listings will be developed for presenting the participant data, including participant identifier, cohort and specific measurement(s).

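### Does SAP 7.5 need to define active hours, and list them with the valid-day count beside each participant's step change?

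*SAP*

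**What the plan says.** Steps and cadence from the activity tracker are secondary assessments (Protocol 2.2.2; SAP 5.2.1). SAP 7.5 gives the derivation:

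- A day is valid if the tracker "records at least 8 active hours during waking hours (7am to 10pm local time for the participant"). Only activity inside that window is analysed.
- At least 4 valid days out of 14 are needed. "If there are fewer than 4 valid days, the average number of steps at baseline will not be calculated", and the same process applies at Week 12.
- Steps: "The number of steps taken is summed up for all the valid days, then averaged over the number of valid days". Daily totals are not scaled for hours.
- Walking duration comes from the start and stop times of the tracker's "recorded activity for each valid day", expressed in minutes per day.
- Cadence then uses that duration as its denominator: "The cadence (in steps/min) for a valid day will be calculated as the number of steps per day divided by the walking duration".

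Protocol 5.1.2 says the device is there to "measure the amount (steps) and intensity (cadence) of daily ambulatory activities".

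On output, SAP section 4 records 5 participants instead of 50 and states that "the pre-planned analyses for this study will not be conducted"; listings replace them. SAP section 7 says customised listings will be developed, "including participant identifier, cohort and specific measurement(s").

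**The concern.** The valid-day rule depends on a term the section never defines. An active hour could be an hour worn, an hour with data recorded, a clock hour containing some activity, or an hour of movement, and a listed step change means something different under each.

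If it is worn or recorded time, a shift in wear between run-in and Week 12 can create or hide a step change, because totals are not scaled. If it is moving time, the hours are partly the outcome, and dividing by them would remove real change. A reader shown neither hours nor valid-day counts cannot tell these cases apart. Cadence could be affected too: if walking duration were the same time as the active hours, it would be steps per recorded minute and not walking intensity.

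At stake is how two secondary measures are read for each participant. Protocol 7.2.1 adds some weight, since it asks for confirmation that less breathlessness is not simply the result of less activity.

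**Working it through.** The plan states no figure to reproduce. The arithmetic below only gauges how far a listed value could move.

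**Inputs from the documents.** Window 7am to 10pm: 22 - 7 = 15 h. Threshold 8 h, so 8/15 = 53.3% of the window. Valid days from 4 to 14 per window. Five participants, listings only.

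**Inputs assumed, absent from the documents.** 400 steps per hour; recorded hours per day; day-to-day SD of steps from 1,000 to 2,500; 3,000 to 8,000 steps per day.

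**1. Wear-time reading, constant step rate.** Relative change = (Week 12 hours / baseline hours) - 1.
- 12 h to 9 h: 4,800 to 3,600 steps = -1,200; 9/12 - 1 = -25%.
- 10 h to 12 h: 4,000 to 4,800 steps = +800; 12/10 - 1 = +20%.
- Extremes: 8/15 - 1 = -46.7%; 15/8 - 1 = +87.5%. These need the average over all valid days to sit at 8 h in one window and 15 h in the other, so they are theoretical limits.

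**2. Number of valid days.** Treating days as independent, the standard error of one person's change is SD × sqrt(1/n1 + 1/n2). With 4 days in both windows instead of 14, it is sqrt(14/4) = 1.87 times larger. At SD 2,000 that is 1,414 against 756 steps; at SD 1,000, 707 against 378; at SD 2,500, 1,768 against 945.

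**3. Which reading fits the text.** The term is used only to decide whether a day counts, against a 15-hour window, with 4 of 14 days sufficing. That is the job of a data-sufficiency rule. Eight hours of actual movement would be more than half the window, in patients selected for breathlessness on activity (mMRC of 2 or more, Protocol 3.3.2). Moving time is therefore the least natural reading.

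**4. Cadence.** If walking duration equalled the active hours, a valid day would hold at least 8 × 60 = 480 minutes. Cadence would be at most 3,000/480 = 6.3, 5,000/480 = 10.4 or 8,000/480 = 16.7 steps/min. Nothing in the SAP equates the two times. It uses different terms for them, derives walking duration from start and stop times, and Protocol 5.1.2 describes cadence as intensity of ambulation. The low figures follow only from that unsupported premise.

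**5. Smaller wording points.** The rule against calculating an average names steps only, but the preceding requirement of 4 valid days for analysis plausibly covers cadence. SAP 6.7 and 7.5 word the window differently: 14 days, or 15 if the survey day is added to the 14 before it. The difference is at most one day and each wording is the same at both visits. Login instructions follow Survey 1 (Protocol 6.2.1), so any baseline time after login is at most part of one day.

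**6. What extra listing columns would change.** Raw mean steps remains the measure, so adding hours and valid-day counts changes no listed step or cadence value.

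**The case for a change.** The strongest argument for a change is that individual values are now the whole output. With no summary or test to absorb noise, each listed change should carry what is needed to read it: a change resting on 4 days is not as firm as one resting on 14, and step 2 shows by how much. The programmer must choose a reading anyway, so writing it down costs one sentence, and hours and counts have to be derived to apply the rule. With the Protocol 7.2.1 activity check dropped, the listing is also the only place left to look.

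Much of this is fair as good practice: a definition and a valid-day count would help a reader. It does not make a defect of the plan. The 7.2.1 check falls with the other planned analyses, so no conclusion about breathlessness depends on these numbers. The wording of SAP section 7 on listing content is open-ended and allows the counts. Three safeguards already limit uneven recording: the 8-hour minimum, the fixed daily window and the 4-day minimum. A steps-per-hour column would depend on whether the device detects wear, which cannot be seen because its name is redacted.

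**Conclusion.** No change to the plan follows. The term is undefined in SAP 7.5, and the visible text does not require hours or valid-day counts in the listings. This is missing detail that analysts fill sensibly when they program the rule, and nothing inferential depends on it. Its reach is the reading of secondary step and cadence changes for 5 listed participants.

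The -25% and +20% illustrations hold only on the wear-time reading with assumed hours and a constant 400 steps per hour; the likely size is unknown. The cadence figures should carry no weight without evidence that the two times are the same.

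The conclusion rests on SAP section 4 standing as written, with listings only. It is also limited by what can be seen: the text of the SAP section on C-PPAC scoring (10.2) and of the protocol's C-PPAC appendix (10.2.2) was not available, and Protocol 5.8 defers to the manufacturer's guidance, so a definition elsewhere cannot be ruled out. If the steps data were ever summarised or tested, the definition would need to be settled first.

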#### 7.7 EXTENT OF EXPOSURE

Exposure will be calculated as the number of days between first and last login with TARA.

#### 7.8 SAFETY ANALYSIS

Safety analysis will be performed as defined in the CSP. All safety analyses will be performed on the ES.

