#### 6.3 SUBJECT SETS ANALYSED

The following subject set will be used in the analysis:

Entered set (ES):
This subject set includes all enrolled subjects with informed consent who completed the baseline
Survey (Survey 1).

The ES will be used for all assessments.

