#### 7.8.1 Adverse Events

Unless otherwise specified, the analyses of AEs will be descriptive in nature. All analyses of AEs will be based on the number of subjects with AEs and NOT on the number of AEs.

The analysis of AEs will be based on the concept of treatment emergent AEs. That means that all AEs that occurred after signing the informed consent until the end of study (Week 12) will be assigned to the treatment observed at baseline (background treatment). Non-treatment-emergent AEs will be assigned to "screening" or "follow-up" (after Week 12).

According to ICH E3 (4), in addition to Deaths and serious adverse events, 'other significant' AEs need to be listed in the clinical study report. These will be any non-serious adverse event that led to an action taken with study drug (e.g. discontinuation or dose reduced or interrupted). An overall summary of adverse events will be presented.

The frequency of subjects with AEs will be summarized by treatment, primary system organ class and PT. Separate tables will be provided for subjects with serious adverse events (SAEs), AEs leading to treatment discontinuation, AEs of at least moderate severity and related AEs.

The system organ classes (SOCs) will be sorted by default alphabetically, PTs will be sorted by frequency (within SOC).

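### SAP 7.8 claims to follow the protocol but runs safety on the Entered Set, so AEs of consented participants who leave before Survey 1 may be omitted; SAP 4 does not declare this

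*SAP*

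**What the plan says.** SAP 7.8 consists of two sentences. The first is "Safety analysis will be performed as defined in the CSP". The second is "All safety analyses will be performed on the ES".

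SAP 6.3 defines the ES as the only analysis set: "This subject set includes all enrolled subjects with informed consent who completed the baseline" survey, that is, Survey 1. It adds: "The ES will be used for all assessments".

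SAP 4 gives the declared changes. Because of the sample size ("5 instead of the planned 50 individuals with chronic obstructive pulmonary disease"), "the pre-planned analyses for this study will not be conducted", and listings take their place. It names the primary and secondary assessments and engagement with TARA, and it rules out subgroup analyses. It mentions neither safety nor the safety population.

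SAP 7.8.1 says that, "in addition to Deaths and serious adverse events", other significant "AEs need to be listed in the clinical study report".

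On the protocol side, 7.2.5 includes all study participants in the safety analysis and assigns AEs to the study period from the consent signature.

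**The concern.** The two sentences of SAP 7.8 agree only if everyone who signed consent also completed Survey 1. The SAP does not say that this was so. If anyone consented and left earlier, the ES is smaller than the population the protocol describes for safety, and that person's AEs may be missing from the AE tables and safety listings.

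The loss would be selective in one respect. An AE during run-in counts if the participant goes on to Survey 1, but may drop out if the participant leaves, even when the AE is the reason for leaving. Protocol 3.3.4.2 gives one such route, since SARS-CoV-2 infection leads to discontinuation from the study. That rule applies throughout the study, and the documents show no case of it before Survey 1.

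What is at stake is the completeness of AE reporting in the study report. Deaths and serious AEs matter most here, because SAP 7.8.1 itself says they need to be listed.

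**Working it through.** The plan gives no figure to reproduce, and safety is descriptive, so the check compares definitions and the order of study events.

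**1. Who is in the protocol's safety analysis.** Protocol 7.2.5 says all study participants and does not define the term. The related sections point to consent:
- 7.2.1 includes all enrolled patients in analysis.
- 3.3 equates enrolment with having signed consent and keeps a log of these people whether or not they log in to TARA.
- 6.2.1 calls people participants once they have consented.
- 5.3.7.2 starts AE reporting at consent.
- 3.3 uses a different word, entered, for TARA log-in, and 7.2.5 does not use it.

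**2. Who is in the SAP's safety analysis.** Those with consent and a completed Survey 1 (SAP 6.3, applied by 7.8).

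**3. What lies between the two.** By protocol 6.2.1 the order is: consent, screening survey, tracker shipment, 2-week run-in, Survey 1, TARA login instructions. The gap therefore covers eligible participants who leave during shipment or run-in as well as screen failures. A convention of leaving out screen failures would not explain it, and neither document states one.

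**4. The SAP against itself.** SAP 6.1 starts the safety period at consent, and the AE window in SAP 7.8.1 also starts there. Time counts from consent, but people count only from Survey 1.

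| | Protocol | SAP |
|---|---|---|
| People | All study participants (read as: all who signed consent) | Consent and Survey 1 completed |
| AE start | Consent | Consent |

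**5. Size.** Number affected = N(consented) − N(ES). The ES is a subset of those who consented, so this is at least 0.

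The documents state neither term. The only count is 5 against a planned 50 in SAP 4. Protocol 3.3 defines the 50 as participants entered by TARA log-in. Log-in follows Survey 1, so, leaving aside the consent exclusions in SAP 6.2:

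N(consented) ≥ N(ES) ≥ N(log-in).

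If the 5 counts log-ins, it is a lower bound for both N(consented) and N(ES) and says nothing about their difference. The SAP does not say whether it counts log-ins, the ES or consents.

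**The case against.** **The protocol population is inferred.** 7.2.5 leaves its term undefined, and the start of an AE window says when events count, not whose. This stands as a caution. The consent reading is still the more natural one, because every related section supports it.

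**The ES is openly stated.** SAP 6.3 and 7.8 both name it, so nobody is misled about which set is used. This also stands. What is missing is a statement in SAP 4 that the set departs from protocol 7.2.5. The general sentence there that planned analyses are dropped cannot fill that role, because 7.8 says safety keeps to the protocol.

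**A reader might infer that such an AE would appear in no safety output at all.** The documents do not go that far. SAP 7.8 also invokes the protocol, the listing sentence in 7.8.1 names no analysis set, and protocol 7.2.5 calls for standard sponsor listings whose coverage cannot be seen here. *May be omitted* is as far as the text goes.

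**A reader might infer from 5 against 50 that many people were left out.** That gap is a shortfall in recruitment against plan, not a count of consented participants without Survey 1.

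**A reader might infer that TARA's safety profile is biased.** It is not. TARA login instructions are sent only after Survey 1 (protocol 6.2.1), so any AE lost for lack of Survey 1 precedes access to TARA.

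**Conclusion.** The inconsistency is real and minor. SAP 7.8 cannot both follow protocol 7.2.5 and use the ES unless nobody left between consent and Survey 1, and SAP 4 does not declare the departure. As written, AEs of consented participants who leave during screening, tracker shipment or run-in may be omitted from the AE tables and safety listings.

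The number affected is not stated. If it is zero, no output changes. AEs are still reported individually to the sponsor from consent (protocol 5.3.7.2), and the safety conclusion about TARA stays the same.

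The verdict rests on one assumption: that all study participants in protocol 7.2.5 means everyone who signed consent.

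**What to change.** **Preferred.**
- SAP 6.3: limit the ES rule to assessments other than safety, and define a safety set of all participants who signed informed consent, subject to the consent exclusions in SAP 6.2 (codes B1 and B2).
- SAP 7.8: replace the ES sentence with one that puts all safety analyses on the safety set. Show participants without Survey 1 in a separate category, with no baseline background treatment, and list their deaths, SAEs and other AEs. The category is needed because SAP 7.8.1 groups AEs by background treatment at baseline and SAP 6.7 ties baseline to Survey 1.

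**Alternative.** Keep the AE tables on the ES and say in SAP 4 that this is a change from protocol 7.2.5. Add one listing of all AEs in consented participants outside the ES, with the number of such participants from the enrolment log in protocol 3.3. SAP 6.3 and 7.8 should then refer to that listing.

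Under either option, if nobody is outside the ES, one sentence in the report settles the point.

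**Cost.** A few sentences and one category or listing, possibly empty. The condition is that AEs reported to the sponsor for these participants are available for the study report. Protocol 5.3.7.2 shows that they reach the sponsor on a form, but no section confirms that they are in the analysis database.

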#### 7.8.1 Adverse Events

Unless otherwise specified, the analyses of AEs will be descriptive in nature. All analyses of AEs will be based on the number of subjects with AEs and NOT on the number of AEs.

The analysis of AEs will be based on the concept of treatment emergent AEs. That means that all AEs that occurred after signing the informed consent until the end of study (Week 12) will be assigned to the treatment observed at baseline (background treatment). Non-treatment-emergent AEs will be assigned to "screening" or "follow-up" (after Week 12).

According to ICH E3 (4), in addition to Deaths and serious adverse events, 'other significant' AEs need to be listed in the clinical study report. These will be any non-serious adverse event that led to an action taken with study drug (e.g. discontinuation or dose reduced or interrupted). An overall summary of adverse events will be presented.

The frequency of subjects with AEs will be summarized by treatment, primary system organ class and PT. Separate tables will be provided for subjects with serious adverse events (SAEs), AEs leading to treatment discontinuation, AEs of at least moderate severity and related AEs.

The system organ classes (SOCs) will be sorted by default alphabetically, PTs will be sorted by frequency (within SOC).

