5.3.7.2 Expedited Reporting of AEs and Drug Exposure during Pregnancy to BI Pharmacovigilance

Any AE or SAE must be reported to the sponsor within the timelines listed regardless of causality. The following must be reported by the investigator on the NIS AE form and/or Pregnancy Monitoring Form from signing the informed consent onwards until the end of the study and provided to BI unique entry point:

Type of Report	Timeline	
All serious AEs	immediately within 24 hours	

Clinical Study Protocol Outline

16 Sep 2021

Page 41 of 93

Proprietary confidential information © 2021 Boehringer Ingelheim International GmbH or one or more of its affiliated companies

All non-serious AEs	7 calendar days
Drug exposure during pregnancy	7 calendar days

All SAEs / AEs including those persisting after study completion must be followed up until they are resolved, have been sufficiently characterized, or no further information can be obtained.

The same timelines apply if follow-up information becomes available for the respective events. In specific occasions the Investigator could inform the Sponsor upfront via telephone. This does not replace the requirement to complete and fax the AE form.

Information required

For each reportable adverse event, the investigator should provide the information requested on the AE form.

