6.2 DETAILS OF STUDY PROCEDURES AT SELECTED VISITS

6.2.1 Screening period

Screening Period

The clinical site will identify potential participants for the study. Participants will be approached by the clinical site for participation in the study at one of their regular clinical visits as per the clinical sites' normal practice (e.g. in-person or via telemedicine). The prescribing physician will recommend use of TARA to patients who could benefit from self-management strategies at the same time as provision of a prescription for a once daily maintenance bronchodilator (Spiriva/Stiolto Respimat).

The clinical site will inform the participant about the trial and obtain informed consent in accordance with GCP (ISO 14155) and the local legislation. Once consented, participants will be given a unique ID and a link to the study website where they will log-in to complete a screening survey to ensure all inclusion and exclusion criteria are met.

Once the participant completes the screening survey, they will get a message describing whether or not they are eligible for the study.

Rescreening will be allowed on a case by case basis after discussion between the site and the sponsor.

Clinical Study Protocol Outline

16 Sep 2021

Page 44 of 93

Proprietary confidential information © 2021 Boehringer Ingelheim International GmbH or one or more of its affiliated companies

Activity tracker shipment

Once the participant has signed consent and is determined to be eligible for the study, the activity tracker will be shipped to the study participant. Participants will be requested to wear the activity tracker during the run-in period, for the duration of the study and until the 12-week survey is completed.

Run-in Period

Once participants receive and activate the activity tracker, they will enter a 2-week run-in period. During this time, participants will wear the activity tracker and should take their medication as prescribed.

Pre-TARA Survey 1

Following the run-in period, participants will receive an email asking them to complete the pre-TARA survey. The email will have a link to the survey which will be completed on the study website. Refer to the flow chart for details of which questionnaires will be administered as part of this survey.

Login Instructions

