After completion of pre-TARA survey 1, participants will receive their TARA login instructions via email along with expectations around use. The participant will then be able to login to the TARA web application.

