## 6. GENERAL ANALYSIS DEFINITIONS

#### 6.1 TREATMENT(S)

Treatment specification is not applicable as there are no pharmacological treatments assigned nor administered as part of the study. Analyses will be performed separately by cohort, as different versions of TARA were used.

The following study periods will be defined with respect to safety analyses:

• Post-Informed-Consent: after informed consent

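### SAP 7.8.1 pools adverse events from before and during TARA use under one treatment-emergent label, and its screening category can never be filled

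*SAP*

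**What the plan says.** SAP 7.8.1 adopts the emergent concept outright: "The analysis of AEs will be based on the concept of treatment emergent AEs". The window covers "all AEs that occurred after signing the informed consent until the end of study (Week 12"), and events in it "will be assigned to the treatment observed at baseline (background treatment"). Everything else has two destinations: "Non-treatment-emergent AEs will be assigned to 'screening' or 'follow-up' (after Week 12"). The only safety period defined in SAP 6.1 is "Post-Informed-Consent: after informed consent".

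Protocol 5.3.7.2 sets the reporting window for AEs, "from signing the informed consent onwards until the end of the study". Protocol 6.2.1 gives the order of events after consent: a screening survey, shipment of the tracker to eligible participants, and then the run-in ("Once participants receive and activate the activity tracker, they will enter a 2-week run-in period"). Survey 1 follows, and only then does access open: "After completion of pre-TARA survey 1, participants will receive their TARA login instructions via email".

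The synopsis names TARA as the test product. Protocol 3.3 treats TARA log-in as entry to the intervention. Elsewhere the SAP works from the start of TARA: baseline is tied to TARA initiation (6.7), and exposure runs from first to last log-in (7.7).

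**The concern.** A treatment-emergent window normally opens when exposure to the studied treatment begins, and is meant to separate events that came before from events that came after. Here it opens at a date when nobody has access to TARA. The next sentence of the SAP offers a screening category for events outside the window, although the window's start leaves nothing to put there.

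The study is an uncontrolled pre-post study. Its only within-study reference for adverse events under TARA is the time before TARA. Protocol 1.4.2 places the product's risk in behaviour change that follows engagement with it, so the timing of an event relative to log-in is what a safety reader will look for. Tables that merge the two stretches do not give it. Because SAP 7.8.1 counts participants rather than events, one run-in event is enough to make a participant a treatment-emergent case.

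**Working it through.** The plan states no figure on this point, and safety is descriptive without hypothesis testing (Protocol 7.2.5), so there is no calculation of the plan's to reproduce. The check has three steps.

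**1. Order of events against the window**

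| Step | Source | Inside the SAP 7.8.1 window? | TARA available? |
|---|---|---|---|
| Consent | Protocol 5.3.7.2, 6.2.1 | Window opens | No |
| Screening survey | Protocol 6.2.1 | Yes | No |
| Tracker shipment | Protocol 6.2.1 | Yes | No |
| 2-week run-in | Protocol 6.2.1 | Yes | No |
| Survey 1 | Protocol 6.2.1 | Yes | No |
| TARA log-in and use | Protocol 6.2.2 | Yes | Yes |
| Week 12 (Survey 5) | SAP 6.7 | Window closes | – |

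The Entered Set requires a completed Survey 1 (SAP 6.3), and Survey 1 follows the run-in. On the planned schedule every analysed participant therefore carries the run-in inside the emergent window.

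**2. Can the screening category hold anything?** An event before consent is not reportable under Protocol 5.3.7.2. An event from consent to Week 12 is emergent by SAP 7.8.1. An event after Week 12 goes to follow-up. No time is left over. The screening survey itself comes after consent, so events during screening in the ordinary sense are already counted as emergent.

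**3. Share of the window before TARA.** Inputs: run-in 2 weeks = 14 days (Protocol 6.2.1); intervention 12 weeks = 84 days (Protocol 6.2.2); maximum observation 16 weeks = 112 days from consent to the post-TARA interview (synopsis).

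Share = pre-log-in days / (pre-log-in days + 84)

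- Run-in only, with no time for screening, shipping or survey delay: 14 / (14 + 84) = 14 / 98 = 14.3%.
- One further week before log-in (assumption): 21 / (21 + 84) = 21 / 105 = 20.0%.
- All slack in the 16 weeks placed before log-in (assumption): 28 / (28 + 84) = 28 / 112 = 25.0%.

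Only the first line rests on durations that the documents state. The last is a ceiling rather than an estimate, because the 16 weeks must also hold the follow-up visit, Survey 6 and any interview. These are shares of time. They become shares of events only at a constant event rate, and even then they describe no planned output, since the tables count participants.

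For scale in those tables: SAP 4 gives 5 participants. If all 5 are in the Entered Set, a single participant whose only event fell in the run-in moves the overall treatment-emergent figure by 1/5 = 20 percentage points.

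**The case against.** The strongest reply is that the emergent window matches the treatment the SAP actually names. Events go to background treatment, not to TARA. Protocol 5.3.6 and 5.3.7 define adverse events and causality for a medicinal product. Participants under inclusion criterion 7b already take Spiriva or Stiolto Respimat at entry, those under 7a receive a new prescription around recruitment, and all are to take their medication during the run-in. For the inhaler, run-in events are on treatment. Moving the emergent label to first log-in alone would mark early events on a newly prescribed inhaler as non-emergent. This stands, and it shapes the fix.

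It also rules out two stronger readings that a reader might draw. One is that the SAP credits TARA with events that preceded it. It does not: the sentence that defines the window assigns them to background treatment. The other is that starting at consent is itself an error. Protocol 5.3.7.2, Protocol 7.2.5 and SAP 6.1 all start there, although the protocol calls the span the study period and not treatment-emergent.

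Nor is the pre-TARA reference lost. Onset dates are collected, so the timing can be rebuilt. No document plans a comparison of events before and during TARA. With 5 participants and most analyses reduced to listings (SAP 4), each event can be read individually.

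What the reply does not answer is that the screening category stays empty, that the SAP never says which treatment the emergent label refers to when TARA is the test product and exposure is counted by log-in, and that SAP 7.8.1 still calls for frequency tables in which the two stretches are merged.

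**Conclusion.** The point holds as one of labelling and presentation. SAP 7.8.1 calls the whole span from consent to Week 12 treatment-emergent, leaves the treatment in question unclear, keeps a category that its own rule empties, and plans tables that cannot place an event before or after the start of TARA. At least 14 of 98 days (14%) of the window come before TARA access. This assumes the run-in and intervention last as planned and no time passes between consent and run-in or between Survey 1 and log-in; any such time raises the share by an amount the documents do not give.

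First log-in as the dividing date is inferred from Protocol 3.3 and SAP 6.7 and 7.7; no section names it as the start of the emergent period. The practical weight is modest, given 5 participants and a descriptive analysis, but the correction is nearly free.

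**What to change.** In SAP 6.1 and 7.8.1:

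- State which treatment the term treatment-emergent refers to.
- Keep AE collection from consent and keep the display by background treatment.
- Replace screening with two periods. *Pre-TARA* runs from consent to the day before first TARA log-in, and covers all time for participants who never log in. *On-TARA* starts on the day of first log-in. The follow-up category after Week 12 is outside this point and is left as it is.
- Present AE summaries by these periods within background treatment.
- List each AE with its onset day relative to first log-in. At this sample size the listing is more useful than the tables, because the planned periods differ in length by a factor of 84/14 = 6 and raw participant counts are not comparable between them.

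The cost is SAP wording, one derived variable from a date already needed for SAP 7.7, and one extra split in small tables. Events with an incomplete onset date will need the existing imputation rule (SAP 6.6.3) before they can be placed in a period. No new data are required.
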